TITLE PAGE

Full protocol title: Addressing Disparities in Neuromodulation for Rehabilitation: A Mixed Methods Approach to Optimize Access for Underrepresented Racial Minorities

Protocol Version Date: **12/16/2023**

PI Name: **[name]**

NCT Number: NCT05896202

1) Protocol Title

Addressing Disparities in Neuromodulation for Rehabilitation: A Mixed Methods Approach to Optimize Access for Underrepresented Racial Minorities

2) IRB Review History*

Approved (ID 20230154)

3) Objectives*

We will develop culturally sensitive videos for video-enhanced informed consent (VE-IC) with neuromodulation techniques (i.e., vagus nerve [taVNS] and transcranial magnetic [rTMS] stimulation techniques). We will use these videos in a mixed method study design to examine factors that influence the interest or aversion to participate in neurostimulation research in URM with persistent pain. Findings will provide insight on modifiable factors and recruitment/retention strategies to optimize racial minority representation in neurostimulation research. The videos and data from this project will be used in our future research on neurostimulation, and they will be made available for use by others. This study is part of a larger research agenda designed to inform the development of personalized pain relief programs based on using patient preferences and a mechanistic understanding of the interventions to integrate neurostimulation interventions into multimodal care for persistent pain.

Aim 1: Development of culturally sensitive videos for enhance informed consent with neurostimulation and determination of factors that influence minority interest in participating in neurostimulation research. *We hypothesize that participants will have greater interest in participation and expectations for pain relief with the modality for which they received VE-IC in comparison to modalities without VE-IC.*

Aim 2: Examination of the influence that video enhanced informed consent has on expectations with taVNS and on treatment intended effects. *We hypothesize that individuals who had VE-IC for taVNS will demonstrate greater expectations for pain relief and greater changes in heart rate variability (HRV).*

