Primary Outcome Measure Title: Change in Heart Rate Variability (HRV)

Primary Outcome Measure Description: HRV will be measured with an H10 chest strap device (Polar, Finland)

Primary Outcome Measure Timeframe: at visits 2 and 3, Baseline (15 minutes pre taVNS application) to 15 minutes post 1 hour application of taVNS

Secondary Outcome Measure Title: Change in EXPECT questionnaire scores

Secondary Outcome Measure Description: scores ranging from 0-40 with higher scores representing greater expectations for pain relief

Secondary Outcome Measure Timeframe: at visits 2 and 3, Baseline (pre taVNS application) and repeated post 1 hour application of taVNS

10) Arms and Interventions

All participants will be educated on both neurostimulation modalities (taVNS and TMS). This study will include 2 arms. Group 1 will receive a supplemental video on taVNS, in addition to consent forms and brochures describing both modalities.

Group 2 will only receive the consent forms and brochures describing both modalities. While all participants will provide important feedback on consent forms and brochures for both modalities, Group 1 will provide additional feedback specific to the taVNS video they watched.

We will assess the impact of the taVNS video (by comparing Group 1 to Group 2) on participant expectations and intended effects with a single 60-minute bout of taVNS.

11) Procedures Involved*

Black and Hispanic patients with persistent pain will be recruited for a 2-phased mixed methods study. All data collection will take place at the Lynn Rehabilitation Center. In the first phase, participants will be educated on two neurostimulation modalities (taVNS and TMS).

Educational materials will include 1:1 discussion of a typical consent form for each modality, a brief (2 page) description with pictures for each modality, and the brief video for taVNS for those randomly allocated to Group 1. *The development of these educational resources is a primary objective of this project, and the first few months will be spent consulting with experts to develop these educational resources and to produce the videos.*

Structured interviews and questionnaires will be used to examine participants interest in participating in research for each of the modalities, gather their feedback on each educational tool, and to determine factors that influence their interest. This first phase will take place in a single session, and the session is anticipated to take ~2 hours to complete.

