Participants will be given the choice to complete this first visit in person or via Zoom in order to decrease participation burden. For the second phase, all participants will receive active taVNS, but only Group 2 will receive both active and sham taVNS in a randomized crossover design.

All participants will first complete a pretrial assessment battery, followed by a 60-minute trial of taVNS applied with continuous monitoring of HRV during quiet sitting, and then concluded with a posttrial assessment. The second phase will be completed in two sessions that are anticipated to last ~4 hours each. In summary, participants will complete 3 visits for a total of ~10 hours to complete the study.

	Visit 1	Visit 2	Visit 3
taVNS video (n=12)	Education and baseline	Active taVNS	1-wk follow up
Brochures only (n=12) 6 participants	Education and baseline	Active taVNS	Sham taVNS
6 participants	Education and baseline	Sham taVNS	Active taVNS

A detailed description of each procedure is provided below:

*EXPECT questionnaire*⁷: The EXPECT is a 4-item questionnaire that assesses expectations for pain improvement. Each of the 4 items is scored on an 11-point scale, with 0 being no change and 10 representing complete relief. It is anticipated that this questionnaire will take less than 5 minutes to complete.

Heart rate variability (HRV): HRV will be measured with an H10 chest strap device (Polar, Finland) and will serve as the primary endpoint for response to taVNS in Aim 2. Participants will wear the chest strap continuously throughout the application of taVNS.

taVNS: A portable taVNS Stimulator (Soterix Medical, Woodbridge, NJ) will be used with flexible hydrogel electrodes to administer taVNS at the cymba concha (Figure 2), using monophasic pulses (pulse width:500 μ s; frequency 10 Hz), and delivered up to 200% of the perception threshold, but kept below the pain threshold, for 60 minutes. This device is approved for research purposes, and these parameters have been shown to maximize cardiovagal response with taVNS.⁸ Participants will be quiet sitting in a comfortable chair during the application of taVNS.

Figure 2. taVNS electrode application

Please see the Risks to Subjects section for procedures performed to lessen the probability or magnitude of risks.

12) Data Management*

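### The listed EXPECT endpoint is a pre-to-post taVNS change taken wholly after the video, so it does not measure the expectation effect that Aim 2 predicts

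*Combined protocol and SAP*

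**What the plan says.** Section 3 (Objectives, Aim 2) hypothesises that "individuals who had VE-IC for taVNS will demonstrate greater expectations for pain relief". In that sentence the idea of change is attached to heart rate variability (HRV), not to expectations. Section 10 (Arms and Interventions) gives the comparison: "We will assess the impact of the taVNS video (by comparing Group 1 to Group 2) on participant expectations", together with "intended effects with a single 60-minute bout of taVNS".

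Section 11 (Procedures Involved) places the intervention in the first phase. The educational materials include "the brief video for taVNS for those randomly allocated to Group 1", and "This first phase will take place in a single session". The visit table makes that session visit 1.

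Section 9 (Study Endpoints) lists one EXPECT outcome, "Secondary Outcome Measure Title: Change in EXPECT questionnaire scores", and its timing is "Secondary Outcome Measure Timeframe: at visits 2 and 3, Baseline (pre taVNS application) and repeated post 1 hour application of taVNS".

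For the second phase, Section 11 says "all participants will receive active taVNS, but only Group 2 will receive both active and sham taVNS in a randomized crossover design". The visit table gives Group 1 (n=12) active taVNS at visit 2 and a one-week follow-up at visit 3. Group 2 (n=12) is split 6 and 6 between active-then-sham and sham-then-active. Section 12 (Data Management) describes the quantitative analysis only as descriptive statistics.

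**The concern.** The hypothesis is about how high expectations are after the video. The endpoint, as titled, is about how far expectations move during a stimulation session that comes later. These are different quantities. A video effect already present when the participant sits down for taVNS is in both readings and drops out of the difference. If the endpoint is reported as titled, a lasting benefit of the video would show as about zero, and one that fades during the session would show with the wrong sign.

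The choice of session is also open. The single bout in Section 10 could be visit 2 for everyone, or each participant's active session. At visit 2 the groups differ in stimulation as well as in video exposure. At visit 3 the table shows no taVNS for Group 1, although the endpoint lists pre- and post-taVNS readings at both visits. The Section 11 prose, with a 60-minute trial for all participants and two sessions of about 4 hours each, does not settle the matter.

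**Working it through.** The available text gives no effect size, SD or analysis model for EXPECT, so there is no planned figure to reproduce. The scale is consistent: 4 items x 10 points = 40, matching the 0-40 range in Section 9.

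**Timeline.** Video: visit 1, Group 1 only. Listed EXPECT readings: before and after taVNS, visits 2 and 3. Every listed reading follows the video. The visit 2 pre-taVNS score is the first listed reading after the randomized education and precedes any stimulation in either group.

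**Notation (all values assumed).**
- D: video effect on EXPECT at the visit 2 pre-taVNS reading
- phi: share of D remaining after the session
- A: active-minus-sham difference in EXPECT change
- O: visit 3 minus visit 2 difference in active-session change

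**Expected Group 1 minus Group 2 difference in change.**
- Visit 2, with 6 of 12 in Group 2 on sham: (phi - 1) x D + A/2
- Active sessions, with 6 of 12 in Group 2 active at visit 3: (phi - 1) x D - O/2

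With O = 0:

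| D | phi | A | Change, visit 2 | Change, active sessions | Visit 2 pre-taVNS level |
|---|---|---|---|---|---|
| 8 | 1 | 0 | 0 | 0 | 8 |
| 8 | 0.5 | 0 | -4 | -4 | 8 |
| 8 | 1 | 4 | +2 | 0 | 8 |
| 8 | 0.5 | 4 | -2 | -4 | 8 |
| 0 | any | 4 | +2 | 0 | 0 |
| 8 | 1.5 | 0 | +4 | +4 | 8 |

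The first five rows were checked by simulation: 40,000 trials per setting, 12 per group, SD 10, pre/post correlation 0.7, control mean 18, scores held within 0-40. The results (visit 2 / active sessions) were -0.1/-0.1, -3.7/-3.7, +1.8/-0.1, -1.9/-3.8 and +1.9/0.0. The small departures come from the scale limits; the level contrast for D = 8 was 7.5 to 7.6.

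**Precision of the level contrast.** The 95% half-width is t(0.975, 2n-2) x SD x sqrt(2/n). For n = 12 and SD 10: 2.074 x 10 x 0.408 = 8.5 points.

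| n per group | SD 8 | SD 10 | SD 12 |
|---|---|---|---|
| 10 (2 per group leave after visit 1) | 7.5 | 9.4 | 11.3 |
| 12 (visit table) | 6.8 | 8.5 | 10.2 |
| 14 (all 28 in Section 7 analysed) | 6.2 | 7.8 | 9.3 |

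**Precision of the change contrast.** At SD 10 and correlation 0.7, the SD of the change is 10 x sqrt(2 x 0.3) = 7.75. With 12 per group the half-width is 2.074 x 7.75 x 0.408 = 6.6 points.

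**The case against.** The best defence is that this is loose titling. The EXPECT timeframe lists two readings and, unlike the HRV entry, is not written as an interval. The subtraction comes from one word in the title, and Section 10 promises a comparison of expectations without mentioning change. A descriptive table of all scheduled scores would show the level difference. This stands as a limit on the damage: the needed reading is already collected. It does not remove the fault, because nothing in the available text names that level as the outcome, and choosing it after the data are seen would be a post hoc switch.

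A change contrast also answers a legitimate question, namely whether the video alters how expectations respond to a bout of stimulation. If the video effect grows with that experience (phi above 1), the contrast is positive, as the last scenario row shows. That is true, but it is still not the question in Aim 2.

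The magnitudes are assumed, and the illustrative -4 lies inside a half-width of 6.6 points. This also stands: a single trial would give an imprecise negative estimate, not convincing evidence of harm. The recommended endpoint is imprecise too, with a half-width of 8.5 points at SD 10 against an assumed effect of 8.

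Finally, the single bout most naturally means the active one, and then the A/2 term vanishes. That is a fair reading, but the plan does not state it, and 6 of 12 in Group 2 would then have had a sham session first.

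**Conclusion.** The concern holds. As titled, the only EXPECT endpoint measures response to a session and not the effect of the video on expectations. The cancellation is algebraic and does not depend on the assumed effect sizes. With an assumed 8-point video effect, the expected difference in change is 0 if the effect persists and -4 if half fades, when active and sham sessions change EXPECT equally or only active sessions are compared without an order effect. If visit 2 is compared and active exceeds sham by 4 points, the contrast is +2 even when the video does nothing.

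This should be fixed, but the consequence is limited. EXPECT is a secondary outcome, only descriptive statistics are planned, and the data are recoverable. What is at risk is a misleading summary for one stated hypothesis in a study whose stated purpose includes testing educational materials.

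**What to change.** 1. Define the Aim 2 expectation endpoint in Section 9 as the EXPECT score for taVNS at the visit 2 pre-taVNS reading. Report the Group 1 minus Group 2 mean difference with its 95% confidence interval, by randomized group.
2. Keep the pre-to-post change as exploratory, reported separately for active and sham sessions, and state which session any group comparison uses.
3. Reconcile Group 1's visit 3 entry in the table with the Section 11 prose and the Section 9 timeframe.

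The cost is one reworded endpoint entry and one table/prose reconciliation, made before the data are seen. No new data are needed.

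The visit 2 reading has drawbacks. It omits anyone who leaves after visit 1. It may miss an effect that fades between visits, which Section 8 spaces 1-2 weeks apart: if 25% or 50% of an 8-point visit 1 effect has gone, 6 or 4 points remain. Section 23 also has the procedures reviewed again with every participant before the trial phase, which could narrow the group difference. An optional EXPECT at the end of visit 1 would cover these; the form has 4 items and Section 11 puts it at under 5 minutes. It could also serve the Aim 1 comparison of expectations by modality if completed for each modality, since no EXPECT reading is stated for visit 1 in the available text.

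### Aim 1 compares taVNS with TMS within the same person in one session, but the plan neither specifies nor randomises which modality comes first

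*Combined protocol and SAP*

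**What the plan says.** Section 3, Aim 1 states the hypothesis: "greater interest in participation and expectations for pain relief with the modality for which they received VE-IC in comparison to modalities without VE-IC". Section 10 gives a video to one group and for one modality only: "Group 1 will receive a supplemental video on taVNS, in addition to consent forms and brochures describing both modalities". Group 2 gets the written materials on both modalities and no video. In these arms, the only people who have one modality with a video and one without are those in Group 1, so the Aim 1 contrast is taVNS versus TMS within Group 1.

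Section 11 has everyone learn about both modalities: "In the first phase, participants will be educated on two neurostimulation modalities (taVNS and TMS"). This is done through a consent-form discussion and a short illustrated description of each. Group 1 also sees "the brief video for taVNS for those randomly allocated to Group 1". Structured interviews and questionnaires "will be used to examine participants interest in participating in research for each of the modalities". On timing: "This first phase will take place in a single session, and the session is anticipated to take ~2 hours to complete".

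The plan randomises two things: allocation to the taVNS video, and the active/sham order for Group 2 at visits 2 and 3. It does not state the order in which the two modalities are presented or rated at visit 1. Section 12 describes the quantitative analysis as descriptive statistics, with no order term.

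**The concern.** When one person rates two things in one sitting, position can matter. The second set of materials may meet a tired participant, the first may set the anchor for the second, or the last one seen may be freshest at rating. Section 11 leaves position uncontrolled at visit 1, although the plan does control order in the later crossover. If staff settle into a habitual order, the position effect becomes part of the taVNS-minus-TMS difference and cannot be separated from it. Depending on its direction, it could look like support for the Aim 1 hypothesis or hide a real effect of the video.

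**Working it through.** **Inputs.** The table in Section 11 gives 12 participants per group. (Section 7 gives an enrolment of 28 rather than 24; the table is used here.) Section 3, Aim 3 still mentions a TMS-video group; the arms are taken from Sections 10 and 11. The documents give no significance level, SD, effect size or sample-size calculation for Aim 1, so there is no planned figure to reproduce. Assumptions made here: Normal ratings, an order effect that is additive and the same in both groups, illustrative sizes of 0.2 to 0.8 SD, and a two-sided 5% level where an error rate is shown.

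**Step 1: bias.** Let D = rating(taVNS) - rating(TMS), and let o be the shift in a rating from being first rather than second (negative if being second helps). D moves by +o for those who meet taVNS first and by -o for the rest. With a fraction f meeting taVNS first:

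bias in mean D = f·o - (1-f)·o = (2f-1)·o

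| f | bias |
|---|---|
| 0 | -o |
| 0.25 | -0.5·o |
| 0.5 | 0 |
| 0.75 | +0.5·o |
| 1 | +o |

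**Step 2: size against precision, Group 1, common order (f = 1).** The standard error of mean D is SD/√12 = 0.289 SD, so the shift in standard errors is (o/SD)·√12. The last column is the rejection rate of a paired t-test at nominal 5% with no true difference, from the non-central t with 11 df. The plan contains no such test; the column only conveys scale.

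| assumed o | shift in SE | illustrative rejection rate |
|---|---|---|
| 0.2 SD | 0.69 | 9.7% |
| 0.3 SD | 1.04 | 15.8% |
| 0.5 SD | 1.73 | 35.3% |

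**Step 3: what each contrast contains.** Let V be the video effect, M any inherent preference for taVNS over TMS, and f1 and f2 the fractions meeting taVNS first in Groups 1 and 2.

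- Group 1 mean D: V + M + (2·f1 - 1)·o
- Group 2 mean D: M + (2·f2 - 1)·o
- Group 1 minus Group 2: V + 2·(f1 - f2)·o

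Balancing order in Group 1 alone removes the o term but leaves V + M. Subtracting Group 2 removes M, and removes o when the order mix is the same in both groups. If, for example, f1 = 0.75 and f2 = 0.5, a bias of 0.5·o remains.

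**Step 4: simulation check** (40,000 runs, no true difference, o = 0, 0.3, 0.5 and 0.8 SD).

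- Order balanced 6:6 in 12 people, order-specific means averaged: bias 0.00, rejection 4.9% to 5.0%.
- Common order kept, groups compared on D (12 v 12): bias 0.00, rejection 4.9% to 5.1%.

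**Step 5: precision cost** (80% power, Normal approximation).

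- Paired contrast, n = 12: (1.96 + 0.84)/√12 = 0.81 SD of D detectable.
- Between-group difference in D, 12 v 12: (1.96 + 0.84)·√(2/12) = 1.14 SD, larger by a factor of √2.

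**The case against.** The tempting stronger reading is that the plan fixes the order as taVNS then TMS, so that an order effect passes whole into the Aim 1 result. The documents do not support that. The parenthesis in Section 11 lists two modalities and is not a sequence; order may be mixed in practice, and the share carried through is then |2f-1|. Nor does Section 11 say that one modality is taught and rated before the other begins. It lists materials by type, and ratings might follow all the teaching.

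A reader might also infer that the plan carries a stated risk of a false positive for Aim 1. It does not: only descriptive statistics are planned, and the order effects in the working are assumed.

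The strongest defence is that the video is randomised. Section 10 says "We will assess the impact of the taVNS video (by comparing Group 1 to Group 2) on participant expectations", and an order effect common to both groups cancels there. This stands for that comparison. However, Section 10 names it for expectations and intended effects of taVNS, not for interest, and not as the answer to the between-modality hypothesis in Aim 1. The cancellation also needs the same order mix in both groups and a video that does not itself change the order effect; nothing in the plan secures the first.

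It is also fair to say that balancing order would not by itself rescue the Group 1 contrast, because video and modality coincide. That is a reason to change the estimate as well, and the fix does so.

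**Conclusion.** The point holds in a limited form. Modality order at visit 1 is neither specified nor randomised, and the within-person contrast stated in Aim 1 is biased by (2f-1) times any order effect. Under one common order and with 12 people, an assumed effect of 0.2 to 0.5 SD shifts the mean difference by 0.7 to 1.7 standard errors; under an even split the bias is zero. The direction is unknown. The practical harm is a misleading descriptive mean difference.

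The reach is modest. The listed primary outcome is HRV, and the listed secondary outcome is EXPECT change at visits 2 and 3. Section 11 clearly has interest examined for each modality; it is less explicit that expectations are rated for both at visit 1, so the point is firmest for interest. The text between the start of Section 17 and Section 19 was not available to check. The change is worth making because it is nearly free before visit 1 begins and order cannot be randomised afterwards.

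**What to change.** In Section 11, for visit 1:

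- Within each arm, randomise half the participants to have taVNS presented and rated first and half to have TMS first, in balanced blocks. Record the order actually used. In Group 1, show the video with the taVNS materials.
- Report the taVNS-minus-TMS difference in each group as the mean of the two order-specific means.
- Define the Aim 1 video effect as the Group 1 minus Group 2 difference in (taVNS minus TMS) ratings. This also removes any inherent preference for taVNS and any order effect common to both groups. State that both groups rate both modalities on each measure used for Aim 1.

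**Cost.** One more column in the randomisation list and a few sentences of protocol text, with no added visits. Cells are small: 6 per order in each group, and about 3 per cell in Group 2 if order is also balanced across its active/sham split (12/2/2 = 3). The between-group estimate is less precise than the paired contrast (1.14 against 0.81 SD of the difference detectable at 80% power), which should be acknowledged when the result is described.
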